#### 6. DETERMINATION OF PROTOCOL DEVIATIONS

#### 6.1 Definition of Protocol Deviations

Clinical Study Report (CSR) reportable protocol deviations (PDs) are defined in accordance with ICH E3 as important PDs related to study inclusion or exclusion criteria, conduct of the trial, subject management or subject assessment resulting in the potential to jeopardize the safety or rights of the trial subjects or the scientific value of the trial.

All reportable PDs will be evaluated before the analysis and classified according to ICH into the following five categories:

- Subject developed withdrawal criteria during the study but was not withdrawn
  - Underlying medical condition forbidden by the protocol or which may influence immune response.
  - Subject had contraindication for a subsequent study vaccination but was vaccinated
  - Concomitant infection related to the vaccine which may influence immune response.
- Subject received wrong vaccine or incorrect dose
  - Study vaccine was not administered at all
  - Vaccine administration not according to protocol.
- Subject took an excluded concomitant medication
  - Administration of concomitant vaccine(s) forbidden in the protocol.
  - Administration of any medication forbidden by the protocol.
- Subject enrolled and did not satisfy the entry criteria
  - Subject did not meet entry criteria.
- Key study procedures missed or performed out of window
  - Subject did not comply with study vaccination schedule.
  - Subject did not provide any post-vaccination safety data.
  - Subject did not comply with blood draw schedule.
  - Serological results not available post-vaccination.
  - Obvious incoherence, abnormal serology evolution or error in data.

CSR reportable PD will lead to exclusion of the subject or part of the subject's data from at least one analysis set.

The number of subjects in any and by PD category will be summarized by center and overall and individual subject listings will be provided in an appendix.

Prior to the analysis, designated sponsor staff will develop a memo that describes the PDs that lead to exclusions from analysis sets. This memo will be signed off by at least the Biostatistician and the Cluster Physician and will be included in the trial master file (Exclusion Memo).

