# 7.4 Per Protocol Set (PPS), Immunogenicity Set

All subjects in the FAS Immunogenicity set (FAS hSBAVisit5, FAS rSBAVisit5, FAS hSBA Visit 6 and FAS rSBA Visit 6) who:

- Correctly receive the vaccine (i.e., receive the vaccine and at the scheduled time points).
- Have no CSR reportable protocol deviations leading to exclusion (see section 6.2) as defined prior to analysis.
- Are not excluded due to other reasons defined prior to analysis (see section 6.2).

In case of vaccination error, the subject is excluded from the PPS.

If a subject received the correct study vaccine (dose, batch) but from another ongoing study at the site then the subject should be excluded from the PPS.

Similarly to the FAS, the PPS populations will be defined as:

- PPS hSBA Visit 6, primary objective
  - PPS population with subjects that have an evaluable hSBA Visit 6 assessment, one year after completion of a 4-dose infant vaccination series (2, 4, 6 and 12 months of age), for at least one serogroup and have no CSR reportable protocol deviations at that time point
- PPS rSBA Visit 6, primary objective
  - PPS population with subjects that have an evaluable rSBA Visit 6 assessment, one year after completion of a 4-dose infant vaccination series (2, 4, 6 and 12 months of age), for at least one serogroup and have no CSR reportable protocol deviations at that time point
- PPS hSBA Visit 5, secondary objective
  - PPS population with subjects that have an evaluable hSBA Visit 5 assessment, one month after completion of a 4-dose infant vaccination series (2, 4, 6 and 12 months of age), for at least one serogroup and have no CSR reportable protocol deviations at that time point
- PPS rSBA Visit 5, secondary objective
  - PPS population with subjects that have an evaluable rSBA Visit 5 assessment, one month after completion of a 4-dose infant vaccination series (2, 4, 6 and 12 months of age), for at least one serogroup and have no CSR reportable protocol deviations at that time point

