**Table 7.7-3: Immunogenicity Sets** 

PD	PD Description	Study Objective/ Period	All Exposed	FAS Visit 5	FAS Visit 6	PPS Visit 5	PPS Visit 6
code	Exclusion code		EXPFL	FAS10FL	FAS11FL	PPS10FL	PPS11FL
100	Study vaccine not administered AT ALL	All Study	EXC	EXC	EXC	EXC	EXC
110.1	hSBA serological results are not available at Visit 5	Day 331	None	EXC	None	EXC	None
110.2	hSBA serological results are not available at Visit 6	Day 661	None	None	EXC	None	EXC
110.3	rSBA serological results are not available at Visit 5	Day 331	None	EXC	None	EXC	None
110.4	rSBA serological results are not available at Visit 6	Day 661	None	None	EXC	None	EXC
112.1	Obvious deviation from Laboratory Manual or error in laboratory data at Visit 5	Day 331	None	None	None	EXC	None
112.2	Obvious deviation from Laboratory Manual or error in laboratory data at Visit 6	Day 661	None	None	None	None	EXC
140	Vaccination not according to protocol	Day 1 through Day 301	None	None	None	EXC	EXC
140.2	Administration of expired vaccine	Day 1 through Day 301	None	None	None	EXC	EXC
140.3	Administration of lower volume of the study vaccine	Day 1 through Day 301	None	None	None	EXC	EXC
140.4	Incomplete vaccination series	Day 1 through Day 301	None	None	None	EXC	EXC

PD	PD Description	Study Objective/ Period	All Exposed	FAS Visit 5	FAS Visit 6	PPS Visit 5	PPS Visit 6
code	Exclusion code		EXPFL	FAS10FL	FAS11FL	PPS10FL	PPS11FL
150.1	Administration of forbidden vaccine	Before Visit 5 (Day 331)	None	None	None	EXC	EXC
150.2	Administration of forbidden vaccine	Before Visit 6 (Day 661) but After Visit 5 (Day 331)	None	None	None	None	EXC
200	Subject did not meet entry criteria	Day 1	None	None	None	EXC	EXC
220	Subject had contraindication for a subsequent study vaccination but was vaccinated	All Study	None	None	None	EXC	EXC
230.1	Administration of forbidden medication	Before Visit 5 (Day 331)	None	None	None	EXC	EXC
230.2	Administration of forbidden medication	Before Visit 6 (Day 661) but after Visit 5 (Day 331)	None	None	None	None	EXC
240	Underlying medical condition forbidden by the protocol	All Study	None	None	None	EXC	EXC
250.1	Concomitant infection related to the vaccine which may influence immune response	Before Visit 5 (Day 331)	None	None	None	EXC	EXC
250.2	Concomitant infection related to the vaccine which may influence immune response	Before Visit 6 (Day 661) but After Visit 5 (Day 331)	None	None	None	None	EXC

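### SAP Table 7.7-3 code 240 can remove a child from the Visit 5 Per Protocol Set for a condition that begins only after the Visit 5 blood draw

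*SAP*

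**What the plan says.** Table 7.7-3 in SAP V2 section 7.7 gives code 240, "Underlying medical condition forbidden by the protocol", a single row. Its period is All Study. It is marked None for both FAS columns and EXC for both PPS Visit 5 and PPS Visit 6. SAP V1 has the same row.

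Section 7.4 defines the two PPS Visit 5 sets (hSBA and rSBA) as children with an evaluable Visit 5 result "for at least one serogroup and have no CSR reportable protocol deviations at that time point".

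Three other codes in the table are split at Visit 5: 150 (forbidden vaccine), 230 ("Administration of forbidden medication") and 250 ("Concomitant infection related to the vaccine which may influence immune response"). The .1 rows cover events before Visit 5 and exclude from both Per Protocol Sets. The .2 rows cover later events and exclude from PPS Visit 6 only; the period for 150.2 and 250.2 reads "Before Visit 6 (Day 661) but After Visit 5 (Day 331", and 230.2 is equivalent.

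Section 6.1 lists "Underlying medical condition forbidden by the protocol or which may influence immune response" within the category "Subject developed withdrawal criteria during the study but was not withdrawn", the same category as the concomitant infection behind code 250.

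The FAS is primary. The PPS is for sensitivity, for the primary objectives (SAP 8.2.2) and for the secondary ones (protocol 8.4.3.3.2).

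**The concern.** The Day 331 titre is fixed once the blood is drawn, so a condition that begins months later cannot have influenced it. Under the table, membership of PPS Visit 5 nevertheless depends on the child's health over the following 330 days. Valid one-month titres could be dropped, and the set would be selected on a later event.

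There is also a practical risk. SAP 6.2 has the deviation listings programmed from the codes in section 7.7, and SAP 16 names the exclusion files as key programs for peer review. A programmer working from 7.7 and a checker working from 7.4 could set different flags for the same child.

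**Working it through.** **1. The plan's own figure.** The inputs are about 100 evaluable children and 25% drop-out (SAP 5, protocol 8.5). 100 / (1 − 0.25) = 133.3, so 134 against 135 stated; conversely, 135 × 0.75 = 101.25. The design figure reproduces, and n = 100 is used below as an assumed size for PPS Visit 5.

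**2. Which rows let an event after the Visit 5 draw remove that draw?**

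| Code | Period or condition | PPS Visit 5 / PPS Visit 6 | Can a post-Visit 5 event remove Visit 5? |
|---|---|---|---|
| 100 | No study vaccine given | EXC / EXC | No |
| 110, 112, 270 | Tied to one visit | That visit only | No |
| 140, 140.2 to 140.4 | Day 1 to Day 301 | EXC / EXC | No |
| 200 | Day 1 | EXC / EXC | No |
| 260.2 to 260.4 | Visits 2 to 4 | EXC / EXC | No |
| 220 | All Study, but needs a study vaccination, the last at Visit 4 | EXC / EXC | No |
| 150.2, 230.2, 250.2 | Between Visit 5 and Visit 6 | None / EXC | No |
| 240 | All Study | EXC / EXC | **Yes** |

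Code 240 is the only such row.

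**3. One child traced through both rules.** Take a child with four in-window doses, a valid Day 331 sample, and a forbidden condition that begins at Day 500. Under 7.4 the child is in PPS Visit 5; under Table 7.7-3 the child is out. The same child given a forbidden medication at Day 500 (code 230.2) stays in PPS Visit 5.

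**4. Could code 240 mean only conditions present at entry?** Code 200, "Subject did not meet entry criteria", already covers entry failures at Day 1. Section 6.1 places the condition under criteria developed during the study. The Time and Events Table (SAP Table 3-2) marks the exclusion and inclusion criteria again at Visits 5 and 6. So a restriction to entry is not what the SAP describes.

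**5. Size.** The documents give no rate, so assume k = 1 to 3 affected children of n = 100. With x responders among n:

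- Removing k non-responders raises the proportion by x/(n − k) − x/n = xk / [n(n − k)]. This is largest at x = n − k, where it equals k/n.
- Removing k responders lowers it by k(n − x) / [n(n − k)], which is also at most k/n.

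The bound is therefore 1 to 3 percentage points. At 90/100 responders and k = 3, the extremes are 90/97 = 92.8% (up 2.8) and 87/97 = 89.7% (down 0.3).

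Precision, as the width of the Clopper-Pearson 95% interval at about 90% observed:

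| Children removed | n | Responders | Width (points) |
|---|---|---|---|
| 0 | 100 | 90 | 12.7 |
| 1 | 99 | 89 | 12.8 |
| 2 | 98 | 88 | 13.0 |
| 4 | 96 | 86 | 13.2 |

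**The case against.** The strongest reply is that the neighbouring codes differ in kind. A vaccine, a medication or an infection has a date, whereas an underlying condition may be a standing state recognised late. An immunodeficiency diagnosed at Day 500 may well have been present at Day 331, and All Study may simply be the period of detection. This stands for latent and congenital disease, and any split must keep those children out of both sets. It does not justify excluding a child whose condition truly began after Visit 5.

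Second, the time-point clause in 7.4 is loose. Codes 200, 140 and 260 concern earlier events and still exclude from PPS Visit 5, so the clause might only mean deviations assigned to that visit's set. The general bullet in 7.4 has no time limit either. This weakens the conflict with 7.4, but it leaves unexplained why three codes are split and code 240 is not.

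Third, it is not clear that the protocol forbids a condition arising after Visit 5. Protocol 4.2 states the consequence of later meeting a criterion as no further vaccination, and the last dose is at Visit 4. Exclusion criteria 8 and 11, which run for the full study, concern products. That leaves the Day 500 case possible rather than certain. Against it are the criteria check marked at Visits 5 and 6, and the 6.1 wording, which reaches conditions that may influence immune response.

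Fourth, a reader might infer that every child with later onset is misclassified. The documents do not support that. The Cluster Physician and the Clinical Trial Leader first assess which deviations are reportable (SAP 6.2), and 6.1 allows only part of a child's data to be excluded. The review narrows the problem, but it does not alter the table's EXC entry.

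**Conclusion.** The inconsistency is real and minor. Code 240 as tabulated can discard a valid Visit 5 result for a later event, against the time-point definition in 7.4 and the SAP's own convention for codes 150, 230 and 250.

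The reach is the PPS Visit 5 sensitivity analysis of descriptive secondary endpoints. No tests are planned, and the FAS, PPS Visit 6, the primary analysis and the sample size are unaffected. On the assumed 1 to 3 affected children per 100, the shift is bounded at about 1 to 3 points and would usually be smaller.

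A reader might go further and infer biased Visit 5 results, because the interval after Visit 5 is (661 − 331)/660 = 50% of follow-up. The documents do not support this: the length of an interval is not an event rate, and nothing shows that these children's one-month titres would differ from the others'. Selection on later health is a flaw in the definition; no systematic shift has been shown.

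**What to change.** Split the row in Table 7.7-3 before the exclusion file is programmed:

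- **240.1:** condition present, or judged to have been already present, before Visit 5, including latent or congenital conditions diagnosed later. EXC on PPS Visit 5 and on PPS Visit 6.
- **240.2:** onset after Visit 5 and before Visit 6. None on PPS Visit 5, EXC on PPS Visit 6.

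The Cluster Physician and the Clinical Trial Leader would assign onset in the pre-analysis deviation review that SAP 6.2 already requires, and record it in the Exclusion Memo.

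The cost is one extra table row, a small change to the exclusion program, and a medical judgement on onset for each case. Adverse event onset dates are already collected (protocol 3.4.1) and will help, but a recorded date does not settle whether a disease was latent at Visit 5, so this is not purely a programming change.

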#### 8. GENERAL ISSUES FOR STATISTICAL ANALYSES

# 8.1 Adjustment for Covariates

Not applicable.

# 8.2 Handling of Dropouts, Missing Data

First-line analyses will be without missing values.

To minimize the effect of dropouts and missing data the study period will be divided into time intervals for statistical analysis of safety.

# 8.2.1 Safety Data

For solicited adverse events, the solicited study period 30 min - day 7 will be divided into: 30 min, 6h - day 3, day 4 - day 7, and 6h - day 7

No imputation methods will be used to address missing values.

### 8.2.2 Immunogenicity Data

Missing immunogenicity values are considered MCAR and therefore will not contain information that impact the result of the analysis (i.e., not informative). Imputation methods will therefore not be used. The primary objectives will be analyzed using the FAS as the primary population and the PPS for sensitivity.

#### 8.2.3 Efficacy Data

Not applicable.

## **8.3** Multicenter Studies

Center effects will be investigated by applying a 'by center' analysis, i.e., this analysis will be repeated for all centers to investigate if there is any heterogeneity between the participating centers.

# 8.4 Multiple Comparisons and Multiplicity

Not Applicable.

# 8.5 Immunogenicity/Safety/Other Subsets

Not applicable.

# 8.6 Subgroups

Analyses of the primary objectives will be repeated and stratified by center and by sex using the FAS. For details regarding the analyses by center please see section 8.3 above.

# 8.7 Derived and Computed Variables

#### **Demographics**

Body Mass Index (kg/m^2) will be calculated using the following formula:

# **Immunogenicity**

Values below the limit of quantification LQ (recorded as "< LQ") will be set to half that limit (i.e., LQ/2]).

**Titer greater or equal to a given threshold** is defined as binary variable for non-missing values as:

- = 1, if the titer is superior or equal to the given threshold
- = 0, otherwise

#### **Geometric Mean Titer**

The GMT will be calculated using the following formula:

$$\begin{cases} \sum_{i=1}^{n} \log_{10}(t_i) \\ n \end{cases}$$

where  $t_1, t_2, ..., t_n$  are *n* observed immunogenicity titers.

#### **Duration in the Study**

**Duration in the study** is defined in days as:

Last visit date (visit x) $^a$  – Enrollment date (visit 1) + 1

aor premature discontinuation date (in case of withdrawal from the study)

The duration is missing if one of the dates is missing or incomplete.

#### Solicited Adverse Events

For details see section 13.2.

#### Unsolicited Adverse Events

All adverse events will be characterized according to the date of occurrence related to the first vaccination as follows:

- Emergence before vaccination phase: start date before the first date of injection of study vaccine.
- Emergence during vaccination phase: start date on or after the first date of injection of study vaccine or, adverse event increase in severity including to "serious" adverse event.

If start date is equal to the first date of injection then "timing" variable ("On injection day, before injection")"On injection day, after injection") will be used to define whether the adverse event occur before or after the injection.

If there are several vaccinations, the adverse event will be associated with the most recent vaccination.

If an adverse event start date is missing or unknown, the adverse event will be considered as emergent.

When start and/or end dates of an adverse event are only partially known, adverse events will be categorized as emergent before, during, or after vaccination phase using the following rules:

- If the partial end date is before (<) the first study vaccination (i.e., year or year & month is/are before the first study vaccination year or year & month) then the adverse event is emergent before vaccination phase.
- If the partial start date is equal or after (≥) the first study vaccination (i.e., year or year & month is/are after or the same as the first study injection year or year & month) then the adverse event is emergent during vaccination phase.

The **maximum event severity** is the greatest severity associated with a preferred term for a reported adverse event according to the following order: Mild < Moderate < Severe. Unknown/ Missing severity is considered as severe (except for the definition of emergence).

Doc Number: 80333235

Multiple AEs with the same PT for the same subject are counted only once.

**Vaccination-related Adverse Events** are those for which the cause has been evaluated by the investigator, and recorded as possibly related, probably related or unknown/missing.

Safety Laboratory Data

Not applicable

Previous, Concomitant and Post-Vaccination Medications

A **previous medication** is a medication used only before the first study vaccination (i.e. medication end date < first study vaccination date).

A **post-vaccination medication** is a medication used only after study termination (i.e. medication start date > study termination date).

All other medications are **concomitant**.

When start and/or end dates of a medication intake are missing, the medication is considered as concomitant with the study vaccination schedule.

If the first study vaccination date is missing then the medication is considered as concomitant with the study vaccination schedule, provided that the study vaccine was administered to the subject.

#### 8.8 Analysis Software

All analyses will be performed using SAS Software version 9.2 or higher.

#### 8.9 Data Transformation

Distributions of antibodies are generally skewed to the right (Nauta, 2010). Therefore, prior to any statistical analysis that assumes normally distributed observations, antibody titers will be log10-transformed. GMTs and their 95% CIs are computed by exponentiating (base 10) the least squares means and 95% CIs of the log10 titers.

#### 9. STUDY SUBJECTS

# 9.1 Disposition of Subjects and Withdrawals

All subjects who provide informed consent will be accounted for in this study. The frequencies and percentages of subjects in each analysis set, study withdrawals, subgroups, and CSR reportable protocol deviations will also be presented.

The time the subjects are under observation will be summarized using summary statistics (mean, SD, minimum, median, maximum).

#### 10. DEMOGRAPHICS AND OTHER BASELINE CHARACTERISTICS

#### 10.1 Demographics

Age, height, weight and body mass index will be summarized by reporting the mean, standard deviation, median and range, and will be calculated by center and overall.

The frequencies and percentages of subjects by sex, ethnic origin, race will be presented by center and overall. Demographic data will be tabulated for the All Enrolled, FAS Visit 6 (primary population) and Safety sets.

#### **10.2** Medical History

The frequencies and percentages of subjects with medical history will be presented by MedDRA system organ class and preferred term, by center and overall. Medical history data will be tabulated for the All Enrolled, FAS Visit 6 and Safety sets.

#### 11. IMMUNOGENICITY ANALYSIS

#### 11.1 Blood Samples

The frequencies and percentages of subjects with blood draws will be summarized. Data will be tabulated for the enrolled set.

# 11.2 Primary Objectives Analysis

#### **Primary Immunogenicity Objective(s)**

- 1. To evaluate the persistence of the antibody response against *N. meningitidis* serogroups A, C, W and Y at approximately 1 year after completion of a 4-dose infant vaccination series (2, 4, 6 and 12 months of age) of MenACWY vaccine as measured by hSBA titers ≥8.
- 2. To evaluate the persistence of the antibody response against *N. meningitidis* serogroups A, C, W and Y at approximately 1 year after completion of a 4-dose infant vaccination series (2, 4, 6 and 12 months of age) of MenACWY vaccine as measured by rSBA titers ≥8 and ≥128.

#### Primary hypotheses:

No statistical tests will be done.

#### Statistical models:

No statistical models will be applied.

#### Statistical methods:

Analysis of binary data

The primary objective of the study is the persistence one year after the complete schedule of 4 vaccinations, expressed as the number and percentage of subjects with a hSBA titer  $\geq$  8 or a rSBA titer  $\geq$  8 and  $\geq$ 128 at Visit 6.

These percentages will be presented along with associated two-sided 95% Clopper-Pearson confidence intervals.

Handling of missing values for Immunogenicity Data

For immunogenicity data, it may be reasonable to consider missing immunogenicity values as missing completely at random (MCAR), i.e., not informative. Therefore, the

primary analysis will comprise a complete case analysis only, without introducing any bias. Imputation methods will not be used.

Titers below the limit of detection will be set to half that limit for the purposes of analysis.

#### 11.3 Secondary Objectives Analysis

#### Secondary Objective(s)

- 1. To describe hSBA titers ≥8 and hSBA GMTs against N. meningitidis serogroups A, C, W and Y 1 month after a full vaccination series at 2, 4, 6 and 12 months of age.
- 2. To describe rSBA titers ≥8 and ≥128 and rSBA GMTs against N. meningitidis serogroups A, C, W and Y 1 month after a full vaccination series at 2, 4, 6 and 12 months of age
- 3. To evaluate the persistence of the antibody response against N. meningitidis serogroups A, C, W and Y at approximately 1 year after completion of a 4-dose infant vaccination series (2, 4, 6 and 12 months of age) of MenACWY vaccine as measured by hSBA GMTs and rSBA GMTs.

